4.5.1. Safety Variables

The type, incidence, relatedness, and severity of TEAEs and SAEs will be recorded from time of first dosing on day 1 through the follow-up call on Day 3. Refer to Section 3.3 for definitions of AEs, TEAEs, SAE, severity and relatedness.

The following safety laboratory parameters and vital signs will be summarized for baseline and each postdose timepoint collected. Change from baseline will be summarized for all post dose timepoints. The most recent measurement prior to start of infusion of the first ZTI-01 dose will be regarded as baseline. For parameters with multiple pre-dose measurements, screening values prior to the baseline measurement will be listed only.

Serum chemistry:

- Albumin, glucose, blood urea nitrogen (BUN), potassium, magnesium, calcium, sodium, total protein, creatinine, triglycerides, total cholesterol, creatine phosphokinase (CPK), phosphorus, alkaline phosphatase (ALP), aspartate aminotransferase (AST), alanine aminotransferase (ALT), total bilirubin, direct bilirubin, and lactate dehydrogenase (LDH) will be collected at Screening and Day 2 before discharge. Albumin, random glucose, BUN, potassium, magnesium, calcium, sodium, phosphorus, total protein, creatinine, CPK, ALP, AST, ALT, and total bilirubin will be collected at Baseline (Day - 1 to Day 1). Sodium, potassium, magnesium, calcium, and phosphorus will be collected approximately 2 hours prior to the assigned bronchoscopy timepoint.

Hematology:

- Hemoglobin, hematocrit, platelet count, white blood cell (WBC) count, neutrophils, lymphocytes, monocytes, eosinophils, basophils will be collected at Screening and Day 2 before discharge.

Coagulation:

- Prothrombin time (PT) and activated partial thromboplastin time (aPTT) will be collected at Screening and Day 2 before discharge.

Urinalysis:

- Leukocyte esterase, blood, pH, specific gravity, glucose, protein. A microscopic test will be performed if urinalysis is abnormal. The microscopic urinalysis result for the presence of blood will supersede the dipstick urinalysis result. Urinalyses performed at Screening and Day 2 before discharge.

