9.6. Clinical Laboratory Evaluations

Chemistry, Hematology, Coagulation, and Urinalysis laboratory parameters will be collected at Screening, Baseline and Day 2 before discharge as described in Section 4.5.1. Sodium, potassium, magnesium, calcium, and phosphorus chemistry parameters will also be collected approximately 2 hours prior to the assigned bronchoscopy timepoint. The grading scale used for clinical laboratory evaluations is presented in Table 3.

Baseline will be defined as the most recent measurement prior to start of infusion of the first ZTI-01 dose. For parameters with multiple pre-dose measurements, screening values prior to the baseline measurement will be listed only.

The following parameters will be presented (in order):

- Chemistry: Sodium, Potassium, Magnesium, Calcium, Phosphorus, Albumin, Random Glucose, BUN, Total Protein, Creatinine, Triglycerides, Total Cholesterol, CPK, ALP, AST, ALT, Total Bilirubin, Direct Bilirubin, and LDH
- Hematology: Hemoglobin, Hematocrit, Platelet Count, WBC Count, Neutrophils, Lymphocytes, Monocytes, Eosinophils, Basophils
- Coagulation: PT and aPTT
- Urinalysis:
- o By dipstick: Leukocyte Esterase, Blood, pH, Specific Gravity, Protein, Glucose.
- By microscopic evaluation: WBC in urine, Red Blood Cells (RBC) in urine, Bacteria, and Casts.

Laboratory results will be summarized by parameter and severity for baseline and all post-dose timepoints (including maximum severity post-baseline) and presented in Table 20, Table 22, Table 24, and Table 26. At baseline, measurements will be summarized according to the grading scale in Table 3. For post-dose measurements, if a value is outside the normal range but did not meet the definition for an AE due to the value being less than or equal to the measurement at baseline, it will be categorized as "Outside Normal Range." All other values will be summarized according to the grading scale in Table 3.

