Laboratory parameters that have grading criteria for both decreases (result lower than normal range and baseline measurement) and increases (result higher than normal range and baseline measurement) will be summarized separately by direction of change. For example, sodium will be summarized separately as "Sodium, Decrease" and "Sodium, Increase." For the summary of the Urinalysis laboratory parameters, the denominator for WBC in urine and RBC in urine by microscopic evaluation will be the number of subjects with a urinalysis result (dipstick or microscopic evaluation) for the visit, not only the number of subjects with microscopic evaluation.

Abnormal laboratory results, Grade 1 severity or higher, will be listed in Table 16, Table 17, Table 18, and Table 19.

For continuous laboratory parameters, descriptive statistics including mean, SD, median, min and max values by timepoint and change from baseline all post-dose measures will be presented by laboratory parameter in Table 21, Table 23, Table 25, and Table 27.

Data will be visualized using box plots showing the change from baseline at each post dose timepoint.

- Chemistry Parameters: Beginning at Figure 5 and continuing through Figure 23
- Hematology Parameters: Beginning at Figure 24 and continuing through Figure 32
- Coagulation Parameters: Figure 33, Figure 34
- Urinalysis: Figure 35, Figure 36

Only laboratory parameters reported as continuous values will be included in tables of summary statistics and in box plots for change from baseline. Continuous parameters from the urine microscopic evaluation will not be visualized but will be summarized in the tables of summary statistics.

Listing 9, Listing 10, Listing 11, and Listing 12 will provide a complete listing of individual clinical laboratory results with applicable reference ranges.

Baseline serology screening results (Listing 13), urine toxicology and alcohol screening results (Listing 14) will be listed.

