- ^d At unscheduled visits, weight may be performed as part of the physical exam but is not required
- ^e Alcohol history within past 6 months, lifetime tobacco history
- ^fECGs will be performed in the supine or semi-recumbent position (after rest for at least 10 min) at 3 timepoints: at Screening, Day 1 (before first dose of Study Drug), and within 1-2 hours of the last dose (3rd dose) of study drug. In case of premature discontinuation of study drug, ECG is to be performed before discharge.
- ^g At Screening, and before discharge (Day 2), obtain hematology labs (white blood cell count, hemoglobin, hematocrit, and platelet count, neutrophils, lymphocytes, monocytes, eosinophils, basophils); coagulation tests (aPTT and PT), chemistry labs (albumin, glucose, blood urea nitrogen (BUN), potassium, magnesium, calcium, sodium, phosphorus, total protein, creatinine, triglycerides, total cholesterol, CPK, phosphorus, AST, ALT, total bilirubin, direct bilirubin, ALP, LDH), and urinalysis (leukocyte esterase, blood, glucose, protein, pH, and specific gravity via dipstick with addition of urine microscopy if dipstick abnormal). At Baseline (Day -1 to Day 1) obtain albumin, glucose, BUN, potassium, magnesium, calcium, sodium, phosphorus, total protein, creatinine, CPK, AST, ALT, total bilirubin, and ALP. Approximately two hours prior to bronchoscopy (Day 2) obtain sodium, potassium, magnesium, calcium, and phosphorus.
- ^h Serum pregnancy test for women of childbearing potential at screening, and urine pregnancy test for women of childbearing potential at Baseline (Day -1 to Day 1)
- ¹ Alcohol Breathalyzer test, Urine cotinine, and Urine drug screen at Screening and Baseline (Day -1 to Day 1/admission to DEPRU). Cotinine will be reported qualitatively as positive/negative. Urine drug screen will consist of: barbiturates, benzodiazepines, THC, cocaine, opiates, and amphetamine/methamphetamine.
- ^j Subjects will receive a total of three doses of ZTI-01 (fosfomycin disodium) 6g, administered every 8 hours, as 1-hour intravenous infusion ^k Blood sample to determine plasma urea concentration will be obtained just before or during the scheduled bronchoscopy

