14.3.5.3 Urinalysis Results

Table 26: Urinalysis Laboratory Results by Parameter, Maximum Severity, and Timepoint

[Implementation Note: If there are no subjects with an early termination visit, then that row will not be included in the table. If no values are missing for any parameter then that column will not be included in the table. If no values meet the criteria for the "Outside Normal Range" column then exclude column and corresponding footnote.]

Urinalvsis Parameter		N	one	Outside Rai	e Normal nge ^a	M Gra	lild/ ade 1	Mod Gra	erate/ ide 2	Sev Gra	vere/ ade 3	Mi	ssing
Timepoint	Ν	n	%	n	%	n	%	n	%	n	%	n	%
Urinalysis - Any Parameter													
Baseline	x	x	x	NA	NA	x	x	x	x	х	x	х	x
Prior to Discharge (Day 2)	х	x	х	х	х	х	X	x	x	х	х	х	x
Early Termination Visit													
Max Severity Post Baseline													
Protein													
Baseline	х	x	х	NA	NA	х	X	x	x	х	х	х	x
Prior to Discharge (Day 2)	х	x	х	х	х	х	X	x	x	х	х	х	x
Max Severity Post Baseline													
Glucose													
Baseline	х	x	х	NA	NA	х	X	x	x	х	х	х	x
Prior to Discharge (Day 2)	х	x	x	x	х	x	x	x	x	х	x	х	x
Early Termination Visit													
Max Severity Post Baseline													
Notes: N = Number of subjects in the Safety ZTI-01 dose. The "Max Post Baseline" ro ^a Post-dose measurements that were outside "Outside Normal Range"	Population we indicate the normal rate	with clinical ne maximum ange but did	safety labs in n severity ex not meet the	results at the perienced by e definition f	respective s y each subjection an AE du	tudy timepo et at any tim le to the valu	int. Baseline epoint post b ie being less	= The most aseline, incl than or equa	recent meas uding unsch il to the mea	surement pri eduled asses surement at	or to start of ssments. baseline wil	infusion of l be categor	the first ized as

Table 27: Urinalysis Laboratory Summary Statistics by Parameter and Timepoint

[Implementation Note: If there are no subjects with microscopic evaluation then the rows for WBC in Urine, RBC in Urine, and Casts will not be included in table]

			Me	easurement		Change from Baseline				
Timepoint	Ν	Mean	SD	Median	Min, Max	Mean	SD	Median	Min, Max	
pH										
Baseline	х	X.X	X.X	X.X	X.X, X.X	-	-	-	-	
Prior to Discharge (Day 2)	х	X.X	X.X	X.X	X.X, X.X	X.X	X.X	X.X	X.X, X.X	
Specific Gravity										
Baseline	х	X.X	X.X	X.X	X.X, X.X	-	-	-	-	
Prior to Discharge (Day 2)	х	X.X	X.X	X.X	X.X, X.X	X.X	X.X	X.X	X.X, X.X	
WBC in Urine										
Baseline	х	X.X	X.X	X.X	X.X, X.X	-	-	-	-	

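### Table 27 plans means and changes from baseline for urine WBC, RBC and casts, but these are measured only after an abnormal urinalysis, so the rows describe a selected subset of subjects

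*SAP*

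**What the plan says.** - **When microscopy is done.** SAP 4.5.1 states: "A microscopic test will be performed if urinalysis is abnormal". Protocol 8.2.1 has the same rule, and the footnote to the SAP schedule of procedures (Table 1) describes urinalysis as done "via dipstick with addition of urine microscopy if dipstick abnormal".
- **Visits.** SAP 4.5.1: "Urinalyses performed at Screening and Day 2 before discharge". SAP 9.6: "Baseline will be defined as the most recent measurement prior to start of infusion of the first ZTI-01 dose". For urinalysis, baseline is therefore in practice the screening value. SAP 9.6 also lists a Baseline collection but refers back to 4.5.1, which has none for urinalysis. The point is the same either way.
- **What is summarised.** For continuous laboratory parameters SAP 9.6 plans "descriptive statistics including mean, SD, median, min and max values by timepoint and change from baseline all post-dose measures". For microscopy it adds: "Continuous parameters from the urine microscopic evaluation will not be visualized but will be summarized in the tables of summary statistics". The Table 27 shell has baseline and Day 2 rows for WBC, RBC and casts. If no subject at all has microscopy, "then the rows for WBC in Urine, RBC in Urine, and Casts will not be included in table".
- **Missing values.** SAP 6.1 bases continuous summaries on the non-missing sample size. SAP 6.5 rules out imputation of safety values.
- **Denominator rule.** In SAP 9.6, "the denominator for WBC in urine and RBC in urine by microscopic evaluation will be the number of subjects with a urinalysis result", whether by dipstick or microscopy. Casts are not named.

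**The concern.** Clinical laboratory results belong to the safety outcome measure for all dosed subjects (protocol 3.2, SAP 3.2). In these Table 27 rows, whether a subject is counted depends on the result itself: a value exists only if the urinalysis at that visit was abnormal. The visit mean therefore answers a question about subjects with an abnormal urinalysis, not about dosed subjects.

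The change column is narrower still, because it needs microscopy before and after dosing. The treatment-emergent case of main interest, a normal urinalysis at screening and blood or leukocytes on Day 2, has no baseline count and cannot enter. Eligibility makes a clean baseline likely: protocol 5.1 requires no clinically significant findings and 5.2 excludes Grade 2 or higher laboratory values.

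The SAP addresses this selection for percentages through its denominator rule. It leaves it in place for means and changes. At stake is whether a reader of the study report takes a few selected values as the drug's effect on urinary cells in the whole group.

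**Working it through.** The plan states no figure on this point, so there is none to reproduce. Steps 1 and 2 follow from the documents. Steps 3 to 5 are illustrations in which every input except 30 subjects (protocol 11.2) is an assumption.

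**1. Who enters each statistic.**
- Visit mean: subjects with an abnormal urinalysis at that visit (SAP 4.5.1), non-missing values only (6.1), nothing imputed (6.5).
- Change: subjects with microscopy at both visits.
- Normal at baseline and abnormal on Day 2: counted in the Day 2 mean, absent from the change.

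**2. Whether the SAP's own safeguards repair this.** A denominator of all subjects with a urinalysis gives a valid percentage. It cannot give a mean, SD, median or change unless unmeasured subjects are assigned values, which SAP 6.5 does not allow. The Table 27 shell has one N column, defined in its footnote by results at the respective timepoint, so the number behind the change is not shown.

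**3. Visit mean.** Let k of 30 subjects have Day 2 microscopy averaging m RBC/hpf, and let the others truly have u. Table 27 shows m. The all-subject mean is [k × m + (30 − k) × u] / 30.
- k = 2, m = 8, u = 0: (16 + 0)/30 = 0.53, against 8 in Table 27.
- k = 6, m = 20, u = 2: (120 + 48)/30 = 5.6, against 20 in Table 27.

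The direction is upward whenever unmeasured subjects have lower counts on average than measured ones.

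**4. Number with a change.** Let a proportion b be abnormal at baseline and d on Day 2. With independent visits the expected number is 30 × b × d, and the chance that nobody has a change is (1 − b × d)^30.

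| b | d | Day 2 microscopies | Expected with a change | Chance of none |
|---|---|---|---|---|
| 5% | 10% | 3 | 0.15 | 86% |
| 10% | 20% | 6 | 0.6 | 54.5% |
| 20% | 30% | 9 | 1.8 | 16% |

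At the other extreme, if every baseline-abnormal subject is abnormal again on Day 2, the numbers with a change are 1.5 of 3, 3 of 6 and 6 of 9. Even then, 50%, 50% and 33% of the Day 2 microscopies have no change value.

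**5. Effect on the change.** Suppose three subjects go from 1 to 20 RBC/hpf with a normal baseline urinalysis, one goes from 8 to 6 with microscopy at both visits, and 26 stay at 1 without microscopy.

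| | Table 27 | All 30 subjects |
|---|---|---|
| Baseline mean | 8 (n = 1) | (29 × 1 + 8)/30 = 1.2 |
| Day 2 mean | (3 × 20 + 6)/4 = 16.5 (n = 4) | (60 + 6 + 26)/30 = 3.1 |
| Mean change | 6 − 8 = −2 (n = 1) | (3 × 19 − 2)/30 = +1.8 |

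The change has the wrong sign and contradicts the visit means beside it. If the fourth subject had instead gone from 8 to 20, Table 27 would show +12 (n = 1) against (57 + 12)/30 = +2.3. The column can err in either direction.

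**The case against.** **New-onset haematuria is not lost from the safety analysis.** A reader might infer that it is, but the documents do not support that. Protocol 9.2.3 enters any post-dose Grade 1 or higher abnormality on the Appendix B table as an adverse event, and Appendix B grades microscopic blood. Such a case reaches the adverse event tables (Tables 12 and 13), the severity counts in Table 26, Table 19 and Listing 12. This stands, and it limits the point to Table 27. The cover is thinner for WBC and casts, because Appendix B has no specific urine threshold for either.

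**The table does not necessarily flatter the drug.** A reader might infer this from the missing new-onset cases. But the inflated Day 2 mean makes the drug look worse, and step 5 shows the change can err either way.

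**The inflation has no fixed size.** Giving every microscopy 15 RBC/hpf and every other subject 1 would yield all-subject means of 0.10 × 15 + 0.90 × 1 = 2.4 to 0.30 × 15 + 0.70 × 1 = 5.2, and so a multiple of about 6 down to 3. Those inputs are assumed. At baseline, 15/hpf is Grade 2, which protocol 5.2 generally excludes. Microscopy triggered by protein, glucose or leukocyte esterase may also show a normal RBC count.

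**Some new-onset cases do contribute.** A subject whose baseline dipstick was abnormal for another reason has baseline microscopy and so has a change. The exclusion applies to a fully normal baseline urinalysis.

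**The rows may fall away, and nothing formal rests on them.** SAP 9.6 admits only parameters reported as continuous values, so laboratory reporting in ranges would remove them, although the shell plans them. There is no hypothesis test, and the halting rules use graded events. Both observations stand. They lower the consequence but do not make the rows correct.

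**Conclusion.** The point holds for the Table 27 rows for urine WBC, RBC and casts. From the documents' own rules, the visit means cover only subjects with an abnormal urinalysis at that visit. The change omits anyone whose baseline urinalysis was fully normal, and the number of subjects behind the change is not displayed. That the means lie above the all-subject level needs one mild assumption: subjects with a normal urinalysis have lower counts on average.

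The amount of inflation and the net direction of the distortion in the change cannot be derived, because the documents give neither rates of abnormal urinalysis nor cell counts. Under the assumed rates with independent visits, fewer than two of 30 subjects are expected to have a change value.

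The consequence is limited. These are misleading descriptive rows, not a gap in the capture of graded haematuria, and the pharmacokinetic analyses and halting rules are unaffected. The correction is worth making because it is cheap and needs no new data.

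**What to change.** 1. Remove the WBC in Urine, RBC in Urine and Casts rows from Table 27, and replace the SAP 9.6 sentence that sends microscopy parameters to the summary-statistics tables.
2. Show RBC by grade, and WBC and casts as normal or abnormal against the laboratory's reference range, at baseline and Day 2 over all subjects with a urinalysis result. Table 26 can carry this.
3. Extend the SAP 9.6 denominator rule to casts. State that a normal urinalysis with no microscopy required counts as not abnormal. This is an addition, since the present rule names only WBC and RBC and sets a denominator, not a category. An abnormal urinalysis whose required microscopy was not done should count as missing.
4. Keep the individual counts in Listing 12.

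If the Table 27 rows are kept, label them as conditional on microscopy and show a separate n for the change.

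Cost: a short edit to SAP 9.6 and small edits to two table shells, with no new data. Protocol 11.3 plans observed and change summaries for laboratory data generally, so the narrowing should be recorded by the route in SAP section 15. The downside is that no mean cell count is shown for a parameter that was measured selectively.

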9.7. Vital Signs and Physical Evaluations

Vital sign measurements include systolic blood pressure, diastolic blood pressure, heart rate, respiratory rate, peripheral oxygen saturation, and temperature. Vital signs will be assessed at Screening and Baseline visits, immediately prior (within 10 minutes) to each of three doses of study drug, at approximately 0.5, 1, 2, and 5 hours after the start of infusion for each dose, and before discharge on Study Day 2.

The grading scale for vital sign evaluations is presented in Table 4. Summaries of vital signs by severity will be tabulated by timepoint and presented by parameter in Table 28. Vital signs that have grading criteria for both decreases (result lower than normal range and baseline measurement) and increases (result higher than normal range and baseline measurement) will be summarized separately by direction of change.

Descriptive statistics including mean, SD, median, min and max values by timepoint and change from baseline for each post dose timepoint will be presented by parameter in Table 29. The baseline measurement used for all post-dose timepoints will be the most recent measurement prior to start of infusion of the first ZTI-01 dose. Any pre-dose measurements from Screening or Baseline prior to the baseline value will be listed.

Data will be visualized using box plots showing the change from baseline at all post dose study timepoints with lines connecting the median, first quartile, and third quartile of the change from baseline at each timepoint (Figure 37, Figure 38, Figure 39, Figure 40, Figure 41 and Figure 42).

Vital signs results will be listed (Listing 15). Unplanned vital signs measurements will be included in the listing, but excluded from tabular and graphical summaries, except when calculating the maximum severity post-baseline.

The study protocol allows measurements of vital signs to be repeated in the case of an abnormal measurement. Repeat readings may be obtained up to twice more for a maximum of 3 measurements including the initial measurement. The following rules will be used to decide which measurement to include in summaries if more than one replicate was entered into the clinical database.

- If the first replicate is normal, then it will be used for analysis
- If the first replicate is abnormal, and the second replicate is also abnormal, then the first replicate will be used if has a severity equal to or greater to the second replicate, or the second replicate will be used if the second replicate has a higher severity than the first replicate.
- If the first replicate is abnormal, the second replicate is normal, and a third replicate measurement was not performed, then the first replicate will be used in the analysis.
- If the first replicate is abnormal, the second replicate is normal, and the third replicate is normal, then the second replicate will be used in the analysis.
- If the first replicate is abnormal, the second replicate is normal, and the third replicate is abnormal, then the first replicate will be used if has a severity equal to or greater to the third replicate, or the third replicate will be used if the third replicate has a higher severity than the first replicate.

Vital signs replicates not used in the analysis will not be listed.

A physical exam will be performed at Screening, Baseline (Day -1 to Day 1) and Day 2 (day of discharge) as described in Section 4.5, as well as the SAE follow-up as needed. Results of physical examinations, scheduled and unscheduled, will be presented in Listing 16.

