## 27 August 2020

# 8. STUDY PROCEDURES/EVALUATIONS

## 8.1. Clinical Evaluations

Medical history: history or presence of prior and current medical conditions or significant surgical procedures

Physical exam: overall physical assessment (to include vital signs [temperature, blood pressure, respiratory rate, heart rate, peripheral oxygen saturation], skin, head and neck, lungs, heart, liver, spleen, extremities, lymph nodes, and nervous system) and weight will be collected at Screening, Baseline (Day - 1 to Day 1) and Day 2 (day of discharge). Height will be measured and BMI calculated at screening only.

ECG: performed in the supine or semi-recumbent position after resting for at least 10 minutes at 3 timepoints: Screening, Baseline (Day -1 to Day 1), and Day 2 within 2 hours of the third (last) dose of study drug. Each ECG will be interpreted and abnormal results acted upon by the investigator as outlined for each timepoint (Screening and Baseline ECG abnormalities per Exclusion Criteria, Day 2 ECG abnormalities per Appendix B). In case of premature discontinuation, ECG will be performed before discharge.

Vital signs: heart rate, blood pressure, temperature, respiratory rate, and peripheral oxygen saturation will be measured with the subject in the supine or semi-recumbent position, will be obtained at the following timepoints: Screening, Baseline (Day -1 to Day 1), before each of 3 doses of study medication, approximately at 0.5, 1, 2, and 5 hours after the start of each infusion of study drug, and before discharge from DEPRU on Day 2. Since changes in vital signs are expected during bronchoscopy, when a vital sign timepoint is scheduled during a subject's bronchoscopy, that timepoint will be measured immediately before the start of bronchoscopy. If vital signs are abnormal, repeat readings will be obtained up to twice more (total of 3 measurements including the first one), 5-10 minutes apart. If they remain abnormal, unscheduled vital signs will be repeatedly obtained until they normalize (at investigator's discretion).

Prior/Concomitant Medications/Treatments: information regarding allergies and use of prescription medications, non-prescription medications, herbal supplements, nicotine, caffeine, alcohol, and illicit drugs will be obtained at Screening, Baseline (Day -1 to Day 1), Treatment (Days 1-2), Day 2 before discharge, and throughout each subject's enrollment as required.

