#### CONFIDENTIAL

DMID/NIAID/NIH

DMID Protocol 16-0058	Version 9.0
IV Fosfomycin PK Study	27 August 2020

frequency, each AE (by type) will be tabulated by severity, with each occurrence of the AE being counted (same subject can contribute multiple events to frequency). Tabulations of incidence and frequency will be performed separately for AEs overall and for related AEs only.

Observed and change-from-baseline vital signs, laboratory, and ECG data will be summarized using the mean, median, standard deviation, minimum, and maximum. The most recent measurement prior to start of infusion of the first ZTI-01 dose will be regarded as baseline. The number and percentage of subjects with laboratory, vital sign, and ECG abnormalities at baseline, subsequent visits, or early termination from the trial will be tabulated. The results of all laboratory tests, physical exam findings, ECGs, and vital signs will be presented in data listings.

Pharmacokinetics:

The pharmacokinetic outcome measures will be plasma and intrapulmonary PK of ZTI-01.

The following plasma PK parameters will be derived from the plasma concentration vs. time curves for fosfomycin after ZTI-01 administration. Noncompartmental analysis will be used to determine PK parameters, but other modeling techniques can be employed as needed. The below PK parameters will be estimated using Phoenix® WinNonlin® version 8.0 or later, and using plasma concentrations collected after start of the first and/or third doses.

- Maximum measured plasma concentration (Cmax)
- Observed and extrapolated area under the concentration versus time curve (AUC0-8; AUC0-12; AUC0inf)
- Time to peak concentration (tmax)
- Terminal elimination half-life (t1/2)
- Terminal-phase elimination rate constant  $(\lambda_z)$
- Volume of distribution (Vd)
- Clearance (CL)

PK parameters ( $C_{max}$ ,  $t_{max}$ , and AUC0-8) will be compared by dose and the accumulation ratio will be estimated using both  $C_{max}$  and AUC0-8.

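### When the first two vital-sign readings are abnormal, SAP 9.7 ignores a recorded third reading and then leaves it out of the listing

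*SAP*

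**What the plan says.** Protocol 8.1 provides that when vital signs are abnormal, "repeat readings will be obtained up to twice more", 5-10 minutes apart. If they remain abnormal, further unscheduled readings follow at the investigator's discretion. SAP 9.7 restates the limit: "Repeat readings may be obtained up to twice more for a maximum of 3 measurements including the initial measurement".

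SAP 9.7 then gives rules for deciding "which measurement to include in summaries if more than one replicate was entered into the clinical database":

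- First and second abnormal: "If the first replicate is abnormal, and the second replicate is also abnormal, then the first replicate will be used" if its grade is at least that of the second; otherwise "the second replicate will be used if the second replicate has a higher severity than the first replicate". The third reading is not mentioned.
- First abnormal, second normal, third abnormal: the first is used unless the third is worse, in which case "the third replicate will be used if the third replicate has a higher severity than the first replicate".
- First abnormal, second and third normal: the second (normal) reading is used.
- First abnormal, second normal, no third: the first is used.

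The rules close with "Vital signs replicates not used in the analysis will not be listed". Protocol 11.3 says the opposite about listings: "The results of all laboratory tests, physical exam findings, ECGs, and vital signs will be presented in data listings".

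SAP 9.7 also says that unplanned measurements are listed and count toward maximum post-baseline severity, though not in the other summaries. The note to Table 28 names unscheduled assessments in that row and says nothing of unused replicates.

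**The concern.** Vital signs are part of the safety outcome measure (Protocol 3.2, SAP 3.2). The branch for an abnormality that persists over two readings is less sensitive to a worsening third reading than the branch for an intermittent one. Because the unused reading is also left out of Listing 15, a reader of the study report could not see that a worse value was recorded.

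Repeat readings are plausible in this trial. Protocol 2.1 reports decreased heart rate in 28.3% of subjects at 8 g IV in the earlier single-dose study and calls it the most common vital-sign abnormality. Table 28 has 15 scheduled post-baseline rows per vital sign: 4 after dose 1, 5 around each of doses 2 and 3, and 1 before discharge.

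**Working it through.** The plan gives no figure for this rule, so there is none to reproduce.

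**1. Which patterns lose the worst grade.** Apply the SAP 9.7 rule to every grade combination and compare the selected grade with the worst recorded.

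| Pattern (1st, 2nd, 3rd) | Combinations | Worst grade lost |
|---|---|---|
| Abnormal, abnormal, none taken | 9 | 0 |
| Abnormal, abnormal, normal | 9 | 0 |
| Abnormal, abnormal, abnormal | 27 | 5 |
| Abnormal, normal, none taken | 3 | 0 |
| Abnormal, normal, abnormal | 9 | 0 |
| Abnormal, normal, normal | 3 | 3 |

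The five are (1,1,2), (1,1,3), (1,2,3), (2,1,3) and (2,2,3). Taking the worst of all recorded replicates in the abnormal-abnormal branch reduces 5 of 27 to 0 of 27. In the last row the abnormal first reading is set aside by design, but the no-listing sentence hides it too. These are counts of possible patterns, not probabilities.

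**2. Examples with the SAP Table 4 grades.**

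- Systolic hypertension (141-150, 151-160, >160 mmHg): 142, 148, 162 are Grades 1, 1, 3. The rule uses 142, Grade 1.
- Systolic hypotension (85-89, 80-84, <80 mmHg): 88, 87, 78 are Grades 1, 1, 3. The rule uses 88, Grade 1.
- 79, 78, 60 are all Grade 3. The rule uses 79; the grade is right, but the value 60 is neither summarised nor listed.

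**3. Where the third reading could still appear.** The rule feeds Tables 28-29 and Figures 37-42, and Listing 15 omits unused replicates. The unplanned-measurement exception does not clearly restore it, because Protocol 8.1 separates the repeats (up to three readings in all) from the unscheduled readings that follow them. Adverse event outputs would carry the grade only if the investigator recorded an event. Protocol 9.2.3 states automatic entry as an adverse event for laboratory abnormalities of Grade 1 or higher, not for vital signs, and the adverse event shells have no dedicated column for the measured value.

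**4. Possible frequency (assumptions only).** Suppose three independent systolic readings, normal about a stable mean and rounded to whole mmHg, with a third always taken. Let p1, p2, p3 be the probabilities of Grades 1, 2, 3. Given two abnormal readings, the probability that the third exceeds both is

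[p1²(p2 + p3) + (2·p1·p2 + p2²)·p3] / (p1 + p2 + p3)²

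For mean 145 and SD 6, p1 = 0.5937, p2 = 0.1748 and p3 = 0.0049. The numerator is 0.0633 + 0.0012 = 0.0645 and the denominator is 0.7734² = 0.5981, giving 10.8%.

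| SD (mmHg) | Mean 135 | 142 | 145 | 148 | 152 |
|---|---|---|---|---|---|
| 4 | 0.0% | 1.6% | 6.9% | 14.1% | 9.4% |
| 6 | 0.5% | 5.9% | 10.8% | 14.1% | 14.3% |
| 8 | 2.1% | 8.5% | 11.9% | 14.5% | 16.4% |

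A jump of the 1, 1, 3 kind is rarer: at SD 6 it makes up 0.1% (mean 142) to 1.2% (mean 152) of such episodes. A subject whose pressure is really rising would be affected more often than this stable-mean model shows.

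**The case against.** The branches can be read as a two-of-three rule: two abnormal readings settle the matter, and a third decides only when the first two disagree. The blood-pressure note in Table 4 asks for concordant results, and the protocol does not make a third reading mandatory. That is a defensible convention for choosing the analysed value, but the SAP does not state it, and it cannot justify leaving a recorded Grade 3 value out of a listing that the protocol says will be complete.

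Other parts of the objection do stand, and they limit the point:

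- A reader might infer that the worst value disappears from all trial output. The documents do not support that. Table 4 grades vital-sign abnormalities as clinical adverse events, Protocol 9.2.3 requires abnormal findings to be assessed and reported, and Protocol 9.2.1 has doubtful observations reported. A recorded event would reach Tables 11-13 and Listing 8, and Table 15 if moderate or severe and non-serious. The loss is certain only for the vital-sign outputs.
- A reader might infer that severity is understated in everyone who stays abnormal. It is not: 22 of the 27 patterns keep the worst grade, and later unscheduled readings are listed and count toward maximum severity.
- SAP 6.1 is not contradicted. It says only that data are listed in general, and 9.7 is a specific exception. The conflict is with Protocol 11.3.
- The percentages are not trial rates. They are conditional on two abnormal readings, and chronic hypertension is an exclusion criterion.

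**Conclusion.** The point holds for the planned vital-sign outputs. SAP 9.7 ignores a recorded third reading when the first two are abnormal, and its no-listing sentence conflicts with Protocol 11.3. Both follow from the text and need no assumption. The worst grade is lost in 5 of 27 patterns of three abnormal grades; the same sentence also hides the abnormal first reading in the abnormal-normal-normal case.

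How often this would happen is unknown. About 2-16% of episodes with two abnormal readings and a third taken is a conditional range resting on an assumed SD of 4-8 mmHg and mean systolic pressure of 142-152 mmHg; at SD 6 and mean 135 it is about 0.5%.

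This should be fixed but is not critical. Summaries are descriptive, no formal hypothesis is tested, and neither the PK results nor the halting rules use the selected reading. Someone might also want Table 29 rebuilt on first readings; that is a preference, and no separate fault in Table 29 is shown.

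**What to change.** By SAP addendum before data lock (SAP Section 15 rules out amendment afterwards):

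1. In the abnormal-abnormal branch, grade on the worst of all recorded replicates, and state the choice when grades tie.
2. State in the Table 28 note whether the Max Severity Post Baseline row includes all replicates. If it does, add a footnote that it may differ from the timepoint rows, since an abnormal-normal-normal episode would show no grade at its timepoint but a grade in the maximum.
3. Delete the no-listing sentence. List every replicate in Listing 15 with a flag for the one analysed.
4. Add the missing oxygen saturation column to the Listing 15 shell; SAP 9.7 defines it as a vital sign and Figure 41 plots it.

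The cost is SAP wording, programming and one listing shell; no new data are needed. Reported severity may become slightly less favourable.
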